4.2.2 Prohibited concomitant therapy

Other anticancer therapy

If a patient, enrolled in the study, requires the concomitant use of any medication included in Appendix G entitled "List of Prohibited Medications during BYL719 Treatment" (i.e., drugs that are generally accepted by the Qtdrugs.org Advisory Board of the Arizona CERT to have a **known** risk of causing TdP), BYL719 administration must be interrupted as long as the patient requires therapy with the QT prolonging agent. Note Appendix G also prohibits drugs that are substrates for CYP3A and CYP2C with a possible or conditional risk for TdP. If the patient requires long term therapy with such a QT prolonging agent, leading to study treatment interruption of > 28 days, the patient must be permanently discontinued from BYL719.

Herbal medications

Herbal preparations/medications are not allowed throughout the study. These herbal medications include, but are not limited to: medical marijuana, St. John's wort, Kava, ephedra (ma huang), gingko biloba, dehydroepiandrosterone (DHEA), yohimbe, saw palmetto, and ginseng. Patients should stop using these herbal medications 7 days prior to first dose of study drug.

Warfarin and coumarin derivates

Therapeutic doses of warfarin sodium (Coumadin®) or any other coumarin-derivative anticoagulants are not permitted. Warfarin has a narrow therapeutic range and BYL719 is a possible inhibitor of CYP2C8 and 2C9, the major metabolizing enzyme of warfarin. Therapeutic anticoagulation may be accomplished using low-molecular weight heparin.

4.3 Radiation Therapy

Note: Intensity modulated radiation therapy (IMRT) is mandatory for all patients for the initial pelvic field encompassing the gross tumor and at-risk lymph nodes in the pelvis.

Protocol treatment (chemotherapy and radiation therapy) should be initiated simultaneously on a Monday or Tuesday whenever possible

4.3.1 Dose Specifications

Treatment plans for patients on this protocol will consist of 2 phases: 1) the first phase will consist of inverse-planned IMRT-based treatment to the pelvis (rectum and draining lymphatics at risk) for a total of 45 Gy in 1.8 Gy daily fractions, and 2) the second phase will consist of a 3-dimensional conformal boost (a 3-field technique is suggested) to gross disease + a minimum 2 cm margin including all of the presacral space for an additional 5.4 Gy in 1.8 Gy daily fractions.

IMRT Dose Specifications

Inverse planning is required for the IMRT portion of treatment and planning constraints are provided in this section for both the planning target volume (PTV) as well as critical normal structures to be spared. Acceptable treatment plans will be established from a DVH-based analysis of the volumetric dose to both the PTV and critical normal structures to ensure that minimally acceptable constraints for each volume of interest have been met.

IMRT treatment to the pelvis will be planned to deliver a total of 45 Gy to the PTV in 25 fractions of 1.8 Gy over 5 consecutive weeks.

a. Technical Factors

- i. Megavoltage equipment (minimum acceptable energy is 6 MV) capable of delivering static intensity modulation with a multileaf collimator or dynamic intensity modulation (using a multileaf collimator or tomotherapy) is required.
- ii. Inverse-planning capable software is required.

b. Localization, Simulation, and Immobilization

- i. A custom immobilization device (such as Alpha Cradle or vac-loc bag) for supine patients is suggested to minimize setup uncertainty.
- ii. CT-based simulation (maximum 5 mm slice thickness) is required for this protocol and bowel exclusion techniques should be used when possible. Patients may be simulated supine or prone (if a belly board is utilized). Patients should be simulated in the "arms up" position whether prone or supine and with a full bladder.

c. Treatment Planning/Target Volumes

- 2. The definition of volumes will be in accordance with the 1993 ICRU Report #50: Prescribing, Recording and Reporting Photon Beam Therapy.
 - i. The Gross Tumor Volume (GTV) is defined as all known gross disease as determined from a combination of physical exam, colonoscopy, ultrasound, CT (and MRI or PET-CT if performed).
 - ii. The Clinical Target Volume (CTV) is defined as the GTV plus areas considered at significant risk of harboring microscopic disease. The CTV for a T3 tumor should include all gross disease (rectal and nodal) as well as the internal iliac lymph nodes and the mesorectum (perirectal fat and the presacral space). The CTV for a T4 tumor will include the same structures as for a T3 tumor but will include the external iliac lymph nodes as well.
 - iii. The Planning Target Volume (PTV) will provide a margin around the CTV to compensate for the inter- and intra-fraction uncertainty consequent to daily setup uncertainty and to potential internal organ motion. By definition, the PTV will consist of a symmetrical 5 mm expansion around the CTV. In the event that PTVs extend outside of the skin surface, the clinician should manually trim the PTV contours to be 3-5 mm inside the outer skin (unless there is direct skin involvement).
 - 1. The following are guidelines for generating CTV and a unified PTV.
 - a. Rectal GTV (+1.5 cm radially, +2.5 cm craniocaudally) = CTV
 - b. Nodal GTV + 1.5 cm symmetrical expansion = CTV

- c. Uninvolved iliac vessels + 1.0 cm = CTV (include external iliac if T4)
- d. Presacral lymphatic CTV is generated by contouring from mid S1-S5 and 8 mm tissue anterior to the anterior border of the sacral bone
- e. The mesorectum and perirectal lymphatics CTV is generated by utilizing anatomic landmarks:
 - i. Posterior Border: anterior border of the sacrum and gluteus maximus
 - ii. Lateral Border: ileum, piriformis and obturator muscles
 - iii. Anterior Border: should overlap by 1 cm into the bladder, vagina or prostate
- 2. The PTV is generated by expanding all of the above structures by 0.5 cm symmetrically and unifying them into one 3-dimensional volume for planning purposes.
- 3. Examples of contoured patients are available for review on the RTOG website at http://www.rtog.org/CoreLab/ContouringAtlases/Anorectal.aspx. These examples are an excellent resource for the contouring of normal structures as well as GTV, CTV and PTV design.
- 4. PTV planning dose-volume constraints:
 - a. \geq 98% of the PTV receives \geq 93% of the prescribed dose
 - b. $\leq 10\%$ of the PTV receives $\geq 105\%$ of the prescribed dose
 - c. \leq 5% of the PTV receives \geq 110% of the prescribed dose
 - d. None of the PTV is to receive $\geq 115\%$ of the prescribed dose

b. Critical Structures (IMRT Planning Constraints)

- i. Small bowel:
 - 1. No more than 180 cc above 35 Gy
 - 2. No more than 100 cc above 40 Gy
 - 3. No more than 65 cc above 45 Gy
 - 4. No small bowel volume should receive 50 Gy
- ii. Femoral heads:
 - 1. No more than 40% volume above 40 Gy
- 3. No more than 25% volume above 45 Gy
- 4. No femoral head volume should receive 50 Gy
 - i. Bladder:
 - 1. No more than 40% volume above 40 Gy
 - 2. No more than 15% volume above 45 Gy
 - 3. No bladder volume should receive 50 Gy
 - ii. Unspecified Tissue:
- 1. No specific constraints, however a DVH will be generated for "unspecified 2/15/15, 2/19/15, 3/20/15, 3/27/15,4/23/15, 6/11/15, 7/13/15, 8/14/15, 8/17/15, 8/26/15, 8/31/15, 9/3/15, 9/8/15 approved Novartis, 9/11/15, 9/14/15, 9/21/15, RNEXECPI 9/29/15, 10/5/15 novartis, 10/6/15 approved Novartis, 10/8/15, 10/19/12 sent FDA, 11/4/15 clinical hold, 11/5/15 sent Novartis, SMP 11/6/15, 11/20/20/15, Amendment # 1 5/6/16, Amendment # 2 6/2/16, Amendment # 3 10/31/16 –FDA Reviewer edits, Amendment # 3 updated 1/19/2017, Amendment # 4 6/20/17, Amendment # 5 8/9/2017 with IB 10, AMENDMENT #6 1/16/18

tissue" which consists of any tissue within the skin but not contoured as a part of any of the normal structures above and/or the PTV

4.4 Surgery:

Surgery will be performed, according to standard institutional practices, 6-10 weeks after completion of radiation.

5.0 TOXICITIES, DOSE MODIFICATIONS, AND MANAGEMENT

Toxicities will be recorded as adverse events on the Adverse Event case report form and must be graded using The National Cancer Institute's Common Toxicity Criteria (CTCAE) version 4.03 (Appendix C).

5.1 General Principles: This is a phase I study of $5\frac{1}{2}$ weeks of treatment with BYL719 combined with standard capecitabine and radiation. If a dose limiting toxicity occurs, BYL719 will be held until the toxicity reduces to \leq grade 1 at which point patients will be permanently dose reduced by 1 dose level. Patients may continue to receive their capecitabine and radiation as per institutional standard of care when toxicities resolve to \leq grade 2.

IF RADIATION IS NOT GIVEN PATIENT IS TO BE INSTRUCTED TO NOT TAKE CAPECITABINE OR BYL719 DRUGS. See section 4.1 for more details on this.

If treatment is held for more than 28 days, then patient should come off study.

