5.2 Definition of Dose Limiting Toxicities

- Grade 4 neutropenia (ANC < 500/mm³)
- ANC $<1000/\text{mm}^3$ with fever (temp > 101) or infection
- Grade 4 thrombocytopenia: Platelets <25,000/mm³
- Platelets <50,000/mm³ requiring transfusion
- Grade 3 or 4 treatment related non-hematologic toxicities excluding alopecia. Grade 3 nausea, vomiting or diarrhea will only be considered a dose limiting toxicity if it occurs for greater than 48 hours despite maximal medical support. Grade 3 electrolyte abnormalities will not be considered dose limiting toxicities if the electrolyte disorder can be corrected to grade 2 or less within 72 hours. A grade 4 electrolyte abnormality will be considered a DLT.
- Patients who receive < 67% of intended BYL719 or capecitabine secondary to treatment related toxicities will also be considered as having a DLT

During the MTD dose finding portion, patients who are removed from study for reasons other than a DLT, defined in section 5.2, will be replaced.

5.3 Management of Specific Toxicities are outlined below for all patients: most conservative assessments must be used for management and modification:

If a dose limiting toxicity occurs, BYL719 will be held until the toxicity reduces to \leq grade 1 at which point patients will be permanently dose reduced by 1 dose level. Patients may continue to receive their capecitabine and radiation as per institutional standard of care when toxicities resolve to \leq grade 2.

If treatment is held for more than 28 days, then patient should come off study.

During the MTD dose finding portion, patients who are removed from study for reasons other than a DLT, defined in section 5.2, will be replaced.

For toxicities other than dose limiting toxicities, specific dose adjustments, based on the worst preceding toxicity as graded by the NCI Clinical Toxicity Criteria ([NCI-CTCAE version 4.03]), are described below. A maximum of 1 dose reduction of BYL719 from the starting dose may be allowed.

Missed doses of BYL 719 are not made up and BYL719 will be stopped when radiation is completed.

Dose Modifications for BYL719 (TREATMENT RELATED (BYL719)): This table only applies once patient has begun treatment on study and it is only applicable while they are receiving treatment on study		
Worst toxicity (CTCAE 4.03 Grade)	Dose Modifications for BYL719	
HEMATOLOGICAL		
Neutropenia (ANC)		
Grade 3 (ANC < 1.0 - 0.5 x 10 ⁹ /L)	Omit dose until resolved to ≤ Grade 1, then:	

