Grade 4 ANC <0.5 x 10 ⁹ /L without fever) * this is also a DLT*	 If resolved in ≤ 7 days, then maintain dose level If resolved in > 7 days, then ↓ 1 dose level 	
ANC <1.0 x 10^9 /L with fever ($\geq 38.3^{\circ}$ C or a sustained temperature of \geq 38 °C for more than one hour)	(An ANC <1 with fever of >101 or infection is also considered a DLT) Hold BYL719 until resolved, then \checkmark 1 dose level	
Thrombocytopenia (PLT)		
Grade 3 (PLT < 50-25 x 10 ⁹ /L)	 Omit dose until resolved to ≤ Grade 1, then: If resolved in ≤ 7 days, then maintain dose level If resolved in > 7 days, then ↓ 1 dose level 	
Grade 4 (PLT < 25 x 10 ⁹ /L) *this is also a DLT*	Omit dose until resolved to \leq Grade 1, then \bigvee 1 dose level	
RENAL		
Serum creatinine		

Dose Modifications for BYL719 (TREATMENT RELATED (BYL719)): This table only applies once patient
has begun treatment on study and it is only applicable while they are receiving treatment on study

< 2 x ULN	Maintain dose level
2 – 3 x ULN	Omit dose until resolved to \leq grade 1, then:
	 If resolved in ≤ 7 days, then maintain dose level If resolved in > 7 days, then ↓ 1 dose level
Grade 3 (> 3.0 – 6.0 x ULN)	Permanently discontinue BYL719
Grade 4 (> 6.0 x ULN)	Permanently discontinue BYL719

HEPATIC

Bilirubin

(*for patients with Gilbert Syndrome these dose modifications apply to changes in direct bilirubin only)

Grade 1 (> ULN - 1.5 x ULN)	Maintain dose level with LFTs* monitored as per protocol
Grade 2 (> 1.5 - 3.0 x ULN) with ALT or AST \leq 3.0 x ULN	Omit dose until resolved to ≤ Grade 1, then: If resolved in ≤ 7 days, then maintain dose level If resolved in > 7 days, then ↓ 1 dose level
Grade 3 (> 3.0 - 10.0 x ULN) with ALT or AST \leq 3.0 x ULN	 Omit dose until resolved to ≤ Grade 1, then If resolved in ≤ 7 days, ↓ 1 dose level If resolved in > 7 days discontinue patient from BYL719
Grade 4 (> 10.0 x ULN)	Permanently discontinue BYL719

AST or ALT

Confounding factors and/or alternative causes for increased transaminases like concomitant medications, infection, hepato-biliary disorder, obstruction, liver metastasis, etc. should be excluded before dose interruption/reduction

Dose Modifications for BYL719 (TREATMENT RELATED (BYL719)): This table only applies once patient has begun treatment on study and it is only applicable while they are receiving treatment on study		
Grade 1 (> ULN – 3.0 x ULN)	Maintain dose level with LFTs* monitored per protocol	

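### The protocol orders a permanent one-level BYL719 reduction after every DLT, but many rows of its own dose-modification table order the same dose or permanent discontinuation for events that are DLTs

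*Combined protocol and SAP*

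**What the plan says.** The general rule appears three times, in Sections 4.1, 5.1 and 5.3, with no exception by organ or grade. After a DLT, BYL719 is held until the toxicity is Grade 1 or better, "at which point patients will be permanently dose reduced by 1 dose level". Treatment held for more than 28 days takes the patient off study.

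Section 5.2 defines non-hematologic DLTs as "Grade 3 or 4 treatment related non-hematologic toxicities excluding alopecia". The only further qualifications are for Grade 3 nausea, vomiting and diarrhea (a DLT only if lasting over 48 hours despite maximal support) and Grade 3 electrolyte disorders (not a DLT if corrected within 72 hours).

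Section 5.3 then gives a table of BYL719 modifications, headed as covering toxicities related to BYL719. Its lead-in reads "For toxicities other than dose limiting toxicities, specific dose adjustments, based on the worst preceding toxicity". The heading of 5.3 adds that "most conservative assessments must be used for management and modification". The table nevertheless marks some of its own rows with wording such as "this is also a DLT" (Grade 4 platelets). For Grade 3 and Grade 4 creatinine and Grade 4 bilirubin the instruction is "Permanently discontinue BYL719". For Grade 3 bilirubin it is "If resolved in > 7 days discontinue patient from BYL719".

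**The concern.** A Grade 3 or 4 non-hematologic event in a table of BYL719-related toxicities is, with the narrow exceptions above, a DLT under Section 5.2. It therefore falls under the general rule and also under its own table row, and the two often disagree. The disagreement runs both ways: some rows are less strict than the general rule and others are stricter.

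The dose given after a DLT is a patient-safety instruction in a phase I trial whose stated threshold of success is establishing safety. If sites follow different passages, the same event leads to a restart at full dose, a reduced dose or no further drug, depending on which passage is read. That affects patient handling, how much BYL719 is delivered, and the safety profile reported for each dose level under objective 1.2.1. It does not affect whether the event counts as a DLT.

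**Working it through.** **Step 1: compare each row with the general rule.** The count covers the Section 5.3 rows labelled Grade 3 and/or 4 for a non-hematologic toxicity. The LVEF rows and the combined AST/ALT-bilirubin row carry no grade and are left out. The pneumonitis entry applies to any grade and is also left out.

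| Table action | Rows | Count |
|---|---|---|
| Permanent discontinuation | creatinine G3; creatinine G4; bilirubin G4; confirmed glucose G4; other cardiac G4; skin G4; stomatitis G4; other AEs G4 | 8 |
| Discontinuation if not resolved in time | bilirubin G3 (more than 7 days); glucose G3 (21 days of treatment) | 2 |
| Same dose | AST/ALT G3 (delay of 7 days or less); skin G3 (first occurrence) | 2 |
| Same dose at investigator discretion | stomatitis G3 | 1 |
| Agrees with general rule | AST/ALT G4; QTcF (first occurrence); other cardiac G3; diarrhea G3 or higher; other AEs G3 | 5 |

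8 + 2 + 2 + 1 + 5 = 18, so 13 of 18 rows differ from the general rule in at least some circumstances. Among the hematologic rows, ANC below 1.0 with fever and Grade 4 platelets agree with it. The Grade 4 neutropenia row may conflict, but its layout is broken in the text available and it is not counted.

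**Step 2: test whether the protocol settles the conflict.**
- *The table covers only non-DLTs.* That is what the lead-in says. But the table labels some of its rows as DLTs, and every event in the Grade 3-4 creatinine, bilirubin, AST/ALT and skin rows is a DLT under 5.2. On this reading those rows could never be used.
- *The specific row overrides the general rule.* The lead-in says the opposite, because it removes DLTs from the table.
- *The stricter action wins.* The sentence on conservative assessments might mean this but does not say so. If it did, the same-dose instructions for Grade 3 AST/ALT and first Grade 3 skin toxicity could never be used.

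Each reading picks a different governing instruction, and each leaves part of the text without effect.

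**Step 3: illustrate the size in delivered BYL719.** Section 4.1 gives 28 fractions and daily BYL719 from the first to the last radiation day. Starting on a Monday with weekday fractions, 25 fractions end on day 33 and the last three fall on days 36-38, so 38 daily doses are planned. Doses at levels 1, 2 and 3 are 200, 250 and 300 mg; one level lower is 150, 200 and 250 mg. Assumed: event on day 15, hold on days 15-21. That leaves 14 doses before the hold and 17 after it.

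- Discontinued: 14/38 = 36.8%
- Reduced, level 1: (14×200 + 17×150)/(38×200) = 70.4%
- Reduced, level 2: (14×250 + 17×200)/(38×250) = 72.6%
- Reduced, level 3: (14×300 + 17×250)/(38×300) = 74.1%
- Same dose: 31/38 = 81.6%

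If radiation also pauses for those 7 days, 24 doses follow the hold: discontinued 36.8%; reduced 84.2%, 87.4% and 89.5%; same dose 38/38 = 100%.

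Varying the event day, with the 7-day hold kept:

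| Event day | Discontinued | Reduced, no pause | Reduced, radiation pause |
|---|---|---|---|
| 8 | 18.4% | 65.8-71.1% | 79.6-86.4% |
| 15 | 36.8% | 70.4-74.1% | 84.2-89.5% |
| 22 | 55.3% | 75.0-77.2% | 88.8-92.5% |

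**The case against.** The strongest reply is that Section 5.3 does set an order. The general rule comes first, the table is introduced as covering other toxicities, and the heading asks for the most conservative approach. A DLT would then lead at least to hold and reduction, and to discontinuation where the row is stricter. This is a usable reading, but it is not what the text says: the heading speaks of assessments and names no governing instruction, and the table contains rows marked as DLTs.

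A second reply is that DLT rules serve only dose escalation, so the rows would govern in the expansion cohort. Neither the general rule nor the 5.2 definition is limited in that way, and 5.3 is headed as applying to all patients.

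A third is that Section 12 already permits withdrawal for adverse events that rule out further drug, so the discontinuation rows merely refine the general rule. Section 12 rests on the investigator's judgment; the rows are fixed instructions in a table that is said to exclude DLTs.

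Some row-level points do stand:
- The glucose guidance may be adjusted by clinical judgment, and Grade 3 glucose that resolves in 3-5 days is reduced one level, as in the general rule.
- The stomatitis row defaults to a one-level reduction and also covers intolerable Grade 2, which is not a DLT.
- The 28-day limit is a ceiling, not an entitlement. Even so, Grade 3 bilirubin resolving on day 10 would restart at a reduced dose under the general rule and stop under its row.

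The illustration also depends on the hold. In the day-15 case without a radiation pause, a 14-day hold leaves 10 later doses and gives 57-59% if reduced, 20-22 points above discontinuation instead of 34-37. A hold of 24 days leaves none and removes the gap. No row sets discontinuation directly against same dose; for the same-dose rows, the difference from the general rule is 7.5 to 11 points.

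**Conclusion.** The contradiction is real, and the post-DLT instruction cannot be followed consistently as written. The Grade 3 AST/ALT and first Grade 3 skin rows (less strict) and the creatinine and bilirubin rows (stricter) establish it without the rows that are open to argument. In all, 13 of 18 graded rows depart from the general rule: 10 toward discontinuation, 2 toward the same dose and 1 toward the same dose at discretion.

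The delivered-dose figures show only that the choice of passage can matter materially; they rest on an assumed event day and a 7-day hold. The cohort DLT count and the MTD decision are not shown to change, because these events already count as DLTs. The reason to correct the text is safe and uniform handling of patients, and a safety profile by dose level that does not depend on which passage a site followed.

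**What to change.** Reconcile Sections 4.1, 5.1, 5.2 and 5.3. For each 5.3 row whose events meet the 5.2 definition, the sponsor and its clinicians should state whether the row or the general DLT rule governs. The sentence introducing the table should be corrected to match, and the repeated sentence in 4.1 aligned. If the heading on conservative assessments is meant as a tie-break, it should say so. Which action is right for each event is a clinical decision for them. The cost is a wording amendment, with no additional patients or data.

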5.2 Definition of Dose Limiting Toxicities

- Grade 4 neutropenia (ANC < 500/mm³)
- ANC $<1000/\text{mm}^3$ with fever (temp > 101) or infection
- Grade 4 thrombocytopenia: Platelets <25,000/mm³
- Platelets <50,000/mm³ requiring transfusion
- Grade 3 or 4 treatment related non-hematologic toxicities excluding alopecia. Grade 3 nausea, vomiting or diarrhea will only be considered a dose limiting toxicity if it occurs for greater than 48 hours despite maximal medical support. Grade 3 electrolyte abnormalities will not be considered dose limiting toxicities if the electrolyte disorder can be corrected to grade 2 or less within 72 hours. A grade 4 electrolyte abnormality will be considered a DLT.
- Patients who receive < 67% of intended BYL719 or capecitabine secondary to treatment related toxicities will also be considered as having a DLT

During the MTD dose finding portion, patients who are removed from study for reasons other than a DLT, defined in section 5.2, will be replaced.

5.3 Management of Specific Toxicities are outlined below for all patients: most conservative assessments must be used for management and modification:

If a dose limiting toxicity occurs, BYL719 will be held until the toxicity reduces to \leq grade 1 at which point patients will be permanently dose reduced by 1 dose level. Patients may continue to receive their capecitabine and radiation as per institutional standard of care when toxicities resolve to \leq grade 2.

If treatment is held for more than 28 days, then patient should come off study.

During the MTD dose finding portion, patients who are removed from study for reasons other than a DLT, defined in section 5.2, will be replaced.

For toxicities other than dose limiting toxicities, specific dose adjustments, based on the worst preceding toxicity as graded by the NCI Clinical Toxicity Criteria ([NCI-CTCAE version 4.03]), are described below. A maximum of 1 dose reduction of BYL719 from the starting dose may be allowed.

Missed doses of BYL 719 are not made up and BYL719 will be stopped when radiation is completed.

Dose Modifications for BYL719 (TREATMENT RELATED (BYL719)): This table only applies once patient has begun treatment on study and it is only applicable while they are receiving treatment on study		
Worst toxicity (CTCAE 4.03 Grade)	Dose Modifications for BYL719	
HEMATOLOGICAL		
Neutropenia (ANC)		
Grade 3 (ANC < 1.0 - 0.5 x 10 ⁹ /L)	Omit dose until resolved to ≤ Grade 1, then:	
Grade 4 ANC <0.5 x 10 ⁹ /L without fever) * this is also a DLT*	 If resolved in ≤ 7 days, then maintain dose level If resolved in > 7 days, then ↓ 1 dose level 	
ANC <1.0 x 10^9 /L with fever ($\geq 38.3^{\circ}$ C or a sustained temperature of \geq 38 °C for more than one hour)	(An ANC <1 with fever of >101 or infection is also considered a DLT) Hold BYL719 until resolved, then \checkmark 1 dose level	
Thrombocytopenia (PLT)		
Grade 3 (PLT < 50-25 x 10 ⁹ /L)	 Omit dose until resolved to ≤ Grade 1, then: If resolved in ≤ 7 days, then maintain dose level If resolved in > 7 days, then ↓ 1 dose level 	
Grade 4 (PLT < 25 x 10 ⁹ /L) *this is also a DLT*	Omit dose until resolved to \leq Grade 1, then \bigvee 1 dose level	
RENAL		
Serum creatinine		

Dose Modifications for BYL719 (TREATMENT RELATED (BYL719)): This table only applies once patient
has begun treatment on study and it is only applicable while they are receiving treatment on study

< 2 x ULN	Maintain dose level
2 – 3 x ULN	Omit dose until resolved to \leq grade 1, then:
	 If resolved in ≤ 7 days, then maintain dose level If resolved in > 7 days, then ↓ 1 dose level
Grade 3 (> 3.0 – 6.0 x ULN)	Permanently discontinue BYL719
Grade 4 (> 6.0 x ULN)	Permanently discontinue BYL719

HEPATIC

Bilirubin

(*for patients with Gilbert Syndrome these dose modifications apply to changes in direct bilirubin only)

Grade 1 (> ULN - 1.5 x ULN)	Maintain dose level with LFTs* monitored as per protocol
Grade 2 (> 1.5 - 3.0 x ULN) with ALT or AST \leq 3.0 x ULN	Omit dose until resolved to ≤ Grade 1, then: If resolved in ≤ 7 days, then maintain dose level If resolved in > 7 days, then ↓ 1 dose level
Grade 3 (> 3.0 - 10.0 x ULN) with ALT or AST \leq 3.0 x ULN	 Omit dose until resolved to ≤ Grade 1, then If resolved in ≤ 7 days, ↓ 1 dose level If resolved in > 7 days discontinue patient from BYL719
Grade 4 (> 10.0 x ULN)	Permanently discontinue BYL719

AST or ALT

Confounding factors and/or alternative causes for increased transaminases like concomitant medications, infection, hepato-biliary disorder, obstruction, liver metastasis, etc. should be excluded before dose interruption/reduction

Dose Modifications for BYL719 (TREATMENT RELATED (BYL719)): This table only applies once patient has begun treatment on study and it is only applicable while they are receiving treatment on study		
Grade 1 (> ULN – 3.0 x ULN)	Maintain dose level with LFTs* monitored per protocol	
Grade 2 (> 3.0 - 5.0 x ULN) without total bilirubin elevation to >2xULN	Omit dose until resolved to \leq baseline value If treatment delay is \leq 7 days, restart at same dose If resolved in > 7 days, \checkmark 1 dose level	
Grade 3 (> 5.0 - 20.0 x ULN) without total bilirubin elevation to > 2.0 x ULN	Omit dose until resolved to \leq Baseline value, then If treatment delay is \leq 7 days, restart at same dose If resolved in > 7 days, ψ 1 dose level	
Grade 4 (> 20.0 x ULN) without bilirubin elevation to > 2.0 x ULN	Omit dose until resolved to ≤ Grade 1, then V 1 dose level	
AST or ALT and concurrent Bilirubin		
AST or ALT > 3.0 x ULN and total bilirubin > 2.0 x ULN	Permanently discontinue patient from BYL719	

All dose modifications should be based on the worst preceding toxicity.

^a Common Toxicity Criteria for Adverse Events (CTCAE Version 4.03)

*LFTs include albumin, ALT, AST, total bilirubin (fractionated if total bilirubin > 2.0 x ULN), alkaline phosphatase (fractionated if alkaline phosphatase is grade 2 or higher) and GGT. For patients with Gilbert Syndrome: total and direct bilirubin must be monitored, intensified monitoring applies to changes in direct bilirubin only; the monitoring includes the following LFTs: albumin, ALT, AST, total bilirubin (fractionated if total bilirubin > 2.0 x ULN), alkaline phosphatase (fractionated if alkaline phosphatase is grade 2 or higher) and GGT).

Patients with grade 0 or 1 at screening experiencing ALT/AST/bilirubin increase \geq grade 2 the liver function tests must be monitored weekly or more frequently if clinically indicated until resolved to \leq grade 1. In case of any occurrence of ALT/AST/bilirubin increase \geq grade 3 the liver function tests must be monitored weekly or more frequently if clinically indicated until resolved to \leq grade 1; hereafter the monitoring should be continued every other week or more frequently if clinically indicated until the end of treatment with study medication. Patients who discontinued study treatment should be monitored weekly, including LFTs or more frequently if clinically indicated until resolved to \leq grade 1 or stabilization (no CTCAE grade change over 4 weeks).

ENDOCRINE/METABOLIC

Fasting Plasma Glucose (FPG)

Always consider consultation with a diabetologist and recommend/reinforce on lifestyle changes as per ADA, i.e. exercise and dietary advice (e.g. small frequent meals, low carb, high fiber, balancing carbs over the course of the day. Three small meals and 2 small snacks rather than one large meal).

Grade 1 (> ULN - 160 mg/dL)

[> ULN - 8.9 mmol/L]

Maintain dose level, remind patient on lifestyle changes, and recheck within 24 hours:

*if patient has already had a confirmatory FPG check which confirmed grade 1 FPG then just continue to draw FPG weekly as noted in section 6 and at least weekly for 8 weeks then every 2 weeks until FPG resolves to baseline value or normal. Patient's must always have a 24 hour confirmatory FPG prior to moving to weekly FPG labs.

if grade worsens, follow specific recommendations.

*If on re-check FPG is within institutional normal range, no further assessment or any intervention is needed.*If grade 1 is confirmed: If FPG < 140mg/dl, consider adding metformin as per guidance below or in cooperation with a diabetologist.

- If FPG 140-160 mg/dl, **start/intensify** metformin as per guidance below or in cooperation with diabetologist

Metformin 500 mg once daily with dinner. If no gastrointestinal (GI) intolerance after several days, increase to 500 mg bid, with breakfast and dinner. If tolerated, increase to 500 mg with breakfast, and 1000 mg with dinner. If tolerated, 1000 mg bid with breakfast and dinner. If not tolerated, reduce to prior tolerated dose.

*Guidelines above are meant to be adjusted as per investigator's best clinical judgment. If the treating physician, as per their clinical judgment, does not follow the above guidance to treat a FPG grade 1 by starting or intensifying metformin, documentation of this decision needs to be written and kept with the patient study information and submitted to BrUOG.

Check FPG as clinically indicated and at least weekly for 8 weeks, then continue checking at least every 2 weeks. FPG to be checked until value resolves to baseline values.

be sure to send BrUOG all initial and re-check FPG testing

Grade 2 (>160 - 250 mg/dL) [> 8.9 - 13.9 mmol/L] Maintain dose level and remind patient on lifestyle changes, confirm fasting status of the assessment. If non-fasting, re-check within 24 hours.

Dose Modifications for BYL719 (TREATMENT RELATED (BYL719)): This table only applies once patient has begun treatment on study and it is only applicable while they are receiving treatment on study *if patient has already had a confirmatory FPG check which confirmed grade 2 FPG then just continue to draw FPG weekly as noted in section 6 and at least weekly for 8 weeks then every 2 weeks until FPG resolves to baseline value or normal. Patient's must always have a 24 hour confirmatory FPG prior to moving to weekly FPG labs. Exclude confounding factors like e.g. urinary tract infection, consider consultation with a diabetologist and start oral-antidiabetic treatment, e.g. metformin 500 mg bid with breakfast and dinner. If no GI intolerance, increase to 500 mg with breakfast, 1000 mg with dinner. If tolerated, 1000 mg bid with breakfast and dinner. If not tolerated, reduce to prior tolerated dose. Titrate to the maximum tolerated dose over a period of 3 weeks. - if grade worsens or improves then follow specific grade recommendations. If FPG is still rising on maximum tolerated dose of metformin or persistently >160mg/dl (>8.9 mmol/L), add an insulin-sensitizer, e.g. pioglitazone 30 mg (max. dose). All confirmed grade 2: Monitor FPG as clinically indicated and at least weekly until FPG resolves to \leq Grade 1 •If FPG does not resolve to ≤ Grade 1 within 21 days after institution of appropriate anti-diabetic treatment, reduce BYL719 by 1 dose level •Continue with anti-diabetic treatment and check FPG at least weekly for 8 weeks, then continue checking at least every 2 weeks until resolves to grade ≤ 1 . • Alert treating physician if FPG>250mg/dl *be sure to send BrUOG all initial and re-check FPG testing* Omit BYL719 and confirm fasting status of the assessment. If non-Grade 3 (> 250 - 500 mg/dL) fasting, re-check within 24 hours.

[> 13.9 - 27.8 mmol/L]

Exclude confounding factors like e.g. urinary tract infection and consider consultation with a diabetologist.

Or Grade 2 with signs or symptoms of hyperglycemia (e.g., mental status changes, excessive thirst, polyuria)

Administer intravenous hydration and intervention for electrolyte/ketoacidosis/hyperosmolar disturbances as clinically appropriate. Start metformin and titrate as outlined for Grade 2, add pioglitazone as outlined for Grade 2. Insulin may be used for 1-2 days until hyperglycemia resolves, however this may not be necessary in the majority of BYL719 -induced hyperglycemia given the short half-life of BYL719.

- If FPG resolves to ≤ Grade1 within 3-5 days, while off study treatment and on metformin, re-start BYL719 and reduce 1 dose level, continue with anti-diabetic treatment and check FPG at least weekly for 8 weeks, then continue checking at least every 2 weeks until resolves to ≤ grade 1, alert treating physician if FPG>250mg/dl
- If FPG does not resolve to Grade1 within 3-5 days while off study treatment and on metformin, consult a diabetologist for management of diabetes is strongly recommended. If FPG does not resolve to ≤ Grade 1 within 21 days after institution of appropriate anti-diabetic treatment in cooperation with diabetologist and exclusion of confounding factors e.g. urinary tract infection, permanently discontinue patient from BYL719 treatment

Monitor FPG as clinically indicated and at least twice weekly until FPG resolves to \leq Grade 1.

Grade 4 (> 500 mg/dL) [≥ 27.8 mmol/L]

Omit BYL719 confirm fasting status of the assessment. If non-fasting, re-check within 24 hours.

be sure to send BrUOG all initial and re-check FPG testing

Or Grade 3 with signs or symptoms of hyperglycemia (for ex., mental status changes, excessive thirst, polyuria)

Exclude confounding factors like e.g. urinary tract infection.

Consider cooperation with diabetologist, initiate or intensify medication with appropriate anti-diabetic treatment (see Grade 3), re-check within 24 hours.

- If grade improves then follow specific grade recommendations
- If FPG is confirmed at Grade 4 and confounding factors could be excluded, permanently discontinue patient from BYL719

be sure to send BrUOG all initial and re-check FPG testing

A diabetologist consultation should always be considered.

For all grades: instruct patient to follow dietary guidelines according to local and/or institutional standards for management of diabetes mellitus (such as those provided by the American Diabetes Association) during the study, e.g. small frequent meals, low carbohydrate content, high fiber, balancing carbohydrates over the course of the day; three small meals and 2 small snacks rather than one large meal

Guidelines above are meant to be adjusted as per investigator's best clinical judgment. A diabetologist consultation should always be considered. Based on current experience, hyperglycemia usually resolves within a few days after BYL719 omission; temporary omission of BYL719 may be considered as clinically indicated to improve control of hyperglycemia.

Special attention should be paid to the risk of hypoglycemias in patients interrupting BYL719 treatment and receiving insulin or sulfonylurea.

CARDIAC

Cardiac - Left Ventricular systolic dysfunction

Asymptomatic, resting ejection fraction 40-50%; or 10-20% drop from baseline	Maintain dose level, and continue BYL719 with caution Repeat LVEF within 4 weeks or as clinically appropriate
Symptomatic, responsive to intervention, ejection fraction 20-39% or > 20% drop from baseline	-Omit BYL719 until resolved* (as defined below), then ↓ 1 dose level -LVEF measurement to be repeated, if not resolved* within 28 days permanently discontinue patient from BYL719 treatment
Refractory or poorly controlled, ejection fraction < 20%	Permanently discontinue patient from BYL719

^{*}the event is considered resolved when the patient is asymptomatic, has a resting ejection fraction $\geq 40\%$ and $\leq 20\%$ decrease from baseline.

Cardiac – QTc prolongation		
QTcF > 500 ms (≥ Grade 3) or > 60 ms change from baseline	First Occurrence:	
on at least two separate ECGs	Omit BYL719	
	Perform an analysis of serum potassium and magnesium, and if below lower limit of normal, correct with supplements to within normal limits. Concomitant medication usage must be reviewed	
	Perform a repeat ECG within one hour of the first QTcF of > 500ms or >60ms from baseline: if QTcF remains > 500 ms or >60ms from baseline, repeat ECG as clinically indicated, but at least once a day until the QTcF returns to < 480 ms.	
	Seek cardiologist input	
	Once QTcF prolongation has resolved, BYL719 may be restarted at one lower dose level	
	Second Occurrence:	
	Permanently discontinue patient from BYL719	
Other Cardiac Events		
